9. STATISTICAL CONSIDERATIONS	
A. Sample Size.....	
B. Analyses.....	
10. HUMAN SUBJECTS PROTECTIONS.....	
A. Adequacy of Protection Against Risks.....	

	B. Potential Risks to Subjects and Protections.....
	C. Potential Benefits of the Proposed Research
	D. Risk-to-Benefit Ratio.....
	E. Inclusion of Women and Minorities.....
	F. Subject Confidentiality.....
	G. Study Modification/Discontinuation.....
11.	PUBLICATION OF RESEARCH FINDINGS
12.	REFERENCES

SUMMARY

Patient support after stroke requires a long-term commitment, supporting the patient as they move through “nodes” of acute care, post-acute in-hospital care, subacute care (inpatient rehab, extended stay, etc.), and chronic care. The current standard of stroke care is the Joint Commission (JC)-certified Comprehensive Stroke Center or Primary Stroke Center (CSC/PSC) care system, a collection of proven processes of care, but an approach with a focus on acute care (and to a lesser extent the post-acute in-hospital care), with little coordination of care of the patient after discharge. The overall goal of C3FIT is to assess if patient outcomes are improved when the CSC/PSC system is supplemented with an Integrated Stroke Practice Unit (ISPU) system of care, a patient-centric model of care involving the patient’s caregiver that coordinates care from the acute management through the rehabilitation and recovery of the patient.

The specific aim of this project is to assess superiority of patient-centric outcomes between the CSC/PSC and ISPU models in a cluster-randomized pragmatic trial conducted at approximately 18 clinical sites in the United States (US). The primary aim focuses on differences in 12-months post stroke quality of life (QOL) using the Stroke Impact Scale (SIS) and patient function using the Simplified Modified Rankin Scale (smRS). Secondary aims include other patient/caregiver-centered outcomes, including: (1) short-term function and QOL using the SIS and smRS; (2) control of stroke risk factors; (3) mortality, recurrent stroke rates, and hospital readmission rates; (4) Time At Home; (5) patient depression, using the Patient Health Questionnaire (PHQ-9); and (6) caregiver strain, using the Caregiver Strain Index (CSI). Finally, we aim to determine whether there are patient subgroups specifically responsive or resilient to the intervention, according to effect modification by age, race, sex, and socio-economic status (income and education).

Study Design. C3FIT is a multicenter, randomized, single blinded, Phase III, cluster randomized trial. Sites will be stratified by patient admission volume and geographic location; subsequently, each site will be randomized to one of two patient care management strategies: the CSC/PSC versus ISPU model.

Outcomes. C3FIT’s primary outcomes are the SIS and smRS at 12 months.

Sample Size and Population. Based on the primary outcome, the study was originally designed for a total sample size of approximately 1800 patients, with approximately 18 sites. However, due to the challenges of the COVID-19 pandemic the sample size was decreased to 1,262 and the number of sites were increased to 22. The Statistical and Data Coordinating Center (SDCC) at the University of Alabama determined the change in sample size would not influence the study statistical measures and/or study power, and our funder, PCORI, approved of the changes.

Interventions. Coordinated care (including in-home/in-patient rehabilitation and skilled nursing or extended care facility visits) will be provided based on protocol-based coordination of post-acute in-home/facility care for ISPU Site patients, while CSC/PSC patients will be managed per standard CSC/PSC protocol with no additional study related management post discharge. Clinical site personnel will be provided with training specific to the arm to which they are randomized.

Duration. Patients will be followed at the site level for one year after enrollment.

1. **STUDY OBJECTIVES**

The current standard of stroke care is the JC-certified CSC/PSC care system, a collection of proven individual processes of care, but a system that lacks coordination for the post-stroke care of patients. The C3FIT trial serves as the opportunity to assess potential impact on patient QOL and functional outcomes resulting from the improved integration of care provided by the ISPU approach.

C3FIT's overall goal is to assess if patient outcomes are improved when the CSC/PSC system is supplemented with an Integrated Stroke Practice Unit (ISPU) system of care, a patient-centric model of care involving the patient and caregiver/family that coordinates care from the acute management through the rehabilitation and recovery of the patient.

A. Hypotheses

C3FIT's *Primary Hypothesis* is that the ISPU model of care will show improved mean level SIS and smRS scores at 12 months compared to the CSC/PSC model of care.

The *Secondary Hypotheses* are:

- (1) The ISPU approach will improve secondary stroke outcomes relative to the CSC/PSC approach, including: SIS and smRS at 3 and 6 months, risk factor control, stroke recurrence rates, hospital readmission rates, mortality in the first 12 months, time at home, patient depression, and caregiver strain.
- (2) The ISPU benefit in SIS and smRS will persist after the protocol-based post-acute coordination of in-home/facility care is terminated (at 12 months).
- (3) Patient characteristics (specifically age, race, sex, income, and education) will affect the primary or secondary intervention differences.

B. Primary and Secondary Outcomes

Primary and secondary outcomes are documented in Table 1 and described below.

- *Primary outcomes* include patient function and QOL using the SIS and smRS at 12-months post-stroke.
- *Secondary outcomes* are patient/caregiver-centered and include: (1) short-term patient function and QOL using the SIS and smRS (at 3 and 6 months); (2) the proportion of patient with risk factors controlled at target (at 3, 6, and 12 months); (3) mortality in the first 12 months, time to first recurrent stroke, and number of hospital readmissions per participant month over the first 12 months; (4) Time At Home (proportion of survival time spent at home); (5) patient depression, using the Patient Health Questionnaire (PHQ-9; at 3, 6, and 12 months); and (6) caregiver strain, using the Caregiver Strain Index (CSI; at 3, 6, and 12 months).

Table 1. Study Outcome Measures and Assessment Frequency					
C3FIT OUTCOMES	VARIABLES	ASSESSMENT FREQUENCY (By Month)			
		H	3	6	12
Functional Assessment	Stroke Impact Scale	X	X ⁺	X ⁺	X ⁺
Quality of Life	Simplified Modified Rankin Scale	X	X ⁺	X ⁺	X ⁺
Stroke Risk Factors					
(1) Blood pressure control at target*	Standard Systolic and Diastolic Measurement	X	X	X	X
(2) Lipid control at target*	Standard Lipid Panel or, at a minimum, LDL (Blood Draw, repeated only if patient's cholesterol is elevated at baseline, if LDLC%≥70mg/dl, or if patient is on a statin)	X	X	X	X
(3) Diabetes control at target*	Standard HBA1c (Blood Draw, repeated only if patient's blood glucose is elevated at baseline or if HBA1C%≥7mg/dl)	X	X	X	X
(4) Smoking status*	Question(s) to assess patient smoking status	X	X	X	X
(5) Body Mass Index (BMI)*	Weight and hip circumference	X	X	X	X
(6) Diet	Question(s) to assess patient adherence to recommendations of the American Heart Association (AHA).	X	X ⁺	X ⁺	X ⁺
(7) Exercise	Question(s) to assess patient adherence to recommendations of the AHA.	X	X ⁺	X ⁺	X ⁺
Mortality*	Will be assessed at visits. If needed, medical records will be collected from site, and the Adjudication Committee will review.		X	X	X
Recurrent Stroke*			X	X	X
Rehospitalization*			X	X	X
Time at Home	Assesses Time at Home (patient or caregiver home) versus at institution (for hospitalization, IPR, and/or SNF).		X ⁺	X ⁺	X ⁺
Depression (Patient)	Patient Health Questionnaire (PHQ-9)		X	X	X
Caregiver Strain	Caregiver Strain Index		X	X	X
*Results of these measures will be reported back to patient's treatment team for information/action. *SRU only. H: Collected at the Hospital prior to discharge by site personnel IPR: In-patient rehabilitation facility SNF: Skilled Nursing Facility					

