5. MODEL OF CARE – THE ISPU INTERVENTION

The ISPU is an innovative care model that builds on the JC-certified CSC/PSC design by increasing coordination of care using a patient/caregiver-centric design. C3FIT's ISPU two coordinated units, *Stroke Central* and *Stroke Mobile*, are connected by a technology-enabled coordinating bridge, *Stroke Connect* that addresses the entire care continuum for the patient, from acute through hospital care to 1-year post-discharge care. Stroke Central and Stroke Mobile can be thought of as components of Stroke Connect; see Figure 5.

- **Stroke Connect** is comprised of Stroke Central and Stroke Mobile personnel and technology working in synergy to provide coordination and integration of care delivery and communication across the 1-year episode of care (see Figure 4). Stroke Mobile can access Stroke Central's specialist input through this key care coordination system.
- **Stroke Central** is the acute and in-hospital-based component of the ISPU. Responsible for the patient during EMS routing, ED care, and management while in-hospital, Stroke Central is comprised of a licensed health professional Coordinator and many key

Figure 5. Stroke Nodes and Systems of Care: CSC/PSC versus C3FIT's ISPU

[figure not shown]
specialist care delivery professionals. The Acute Stroke Team resides in Stroke Central and includes key personnel and functions of a CSC/PSC (that currently reside in the hospital setting) but in the IPU model also extends coordination of their care delivery into the Subacute and Chronic Nodes for management of care.

- The Acute Stroke Team expands into post-discharge recovery through Stroke Mobile, a care delivery team comprised of a licensed health professional and lay health educator who work directly with the patient and caregiver/family. During monthly visits in their home or care facility, Stroke Mobile's Care Team follows patients through their final phases of in-hospital stay and remains engaged during any post-hospital care at a rehabilitation unit or extended care facility and/or in their home. Stroke Mobile can access Stroke Central's specialist input virtually at any time through C3FIT's key care coordination system, Stroke Connect.

Technological facilitators will be utilized as part of the Stroke Connect coordination and integration mechanism, including:

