10. HUMAN SUBJECTS PROTECTIONS

This protocol and the informed consent document (Appendix A) and any subsequent modifications will be reviewed and approved by the Steering Committee, IRB, and DSMB responsible for oversight of the study. A signed consent form will be obtained from the subjects.

The total sample size for the primary outcome for this study will be approximately 1800 patients (approximately 100 patients at each clinical site, although some sites will enroll up to 140 consented participants due to limited enrollment by other sites due to institutional COVID PANDEMIC issues) who have consented to participate.

- Participating patients at a clinical site randomized to ISPU arm will be followed by Stroke Central to collect the same acute in-hospital metrics to measure care quality, health status, and outcomes and will also be contacted via telephone by the blinded personnel at the UAB SDCC SRU to assess primary outcomes. However, ISPU patients will also be assessed monthly by Stroke Mobile for 1-year in their home to collect specific metrics that will evaluate the patient and caregiver/family for potential issues and provide follow-up care and targeted education and support.
- The patient and their caregiver (or their legally authorized representative, if patients are unable to provide consent) will be approached to participate in the study ideally during hospitalization or within 5 business days of hospital discharge ideally (to a

maximum of 14 total days) to allow for data collection of specific acute in-hospital metrics. Caregivers may be consented at any time during the C3FIT study, but no data will be collected until consent is obtained. At research visits, the following will be obtained: (1) demographic and other data collection; (2) follow-up data collection specific to the ISPU arm; and (3) contact via telephone survey to collect SIS and smRS outcome data.

- C3FIT's population will include patients with all stroke subtypes and levels of severity, regardless of gender, race, ethnicity, or socioeconomic status. Each Site will recruit from their geographically eligible patients (who have a discharge diagnosis of stroke according to their ICD-10 code) until approximately 100 patients are consented, although some sites will enroll up to 140 consented participants due to limited enrollment by other sites due to institutional COVID PANDEMIC issues.

A. Adequacy of Protection Against Risks

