Recruitment and Informed Consent. The acute in-hospital study sample will include patients admitted to the hospital with suspected stroke symptoms. Potential participants (both patient and caregiver if available) will be approached for recruitment ideally within 5 business days post discharge ideally (to a maximum of 14 total days) for the participant. In the event that the patient is unable to provide consent, their surrogate can be consented. Patients will be identified by study personnel from ED and stroke service admission logs; pilot data suggests nearly complete case ascertainment. To assure that acute in-hospital recruitment and informed consent procedures are followed consistently across Sites, a guidance document will be prepared in consultation with Site PI's and other patient, caregiver and organizational stakeholders, and Site personnel will be trained consistently by CCC staff.

The post-hospital discharge study sample will include patients and caregivers who have a discharge diagnosis of stroke and who reside in each clinical site's defined geographic area. Potential participants will be approached prior to hospital discharge regarding their interest in participating in the study, and every effort will be made to consent both patient and caregiver at that time.

Patients and caregivers at an ISPU Site who participate in Stroke Mobile will receive 12 in-home visits from Stroke Mobile. At each visit, Stroke Mobile will conduct a physical assessment and administer specific clinical scales to determine functional status, medication adherence, fall risk, daily activity level, depression, and caregiver strain, among others. A phlebotomy (draw blood) will occur (cholesterol and HbA1c) according to the study time schedule.

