5. MODEL OF CARE – THE CSC/PSC ARM

Post-discharge, management and treatment of patients in the CSC/PSC arm will follow general clinical practice guidelines as is usually provided by the site in the management of all patients following a stroke, e.g. one-month clinic follow-up by a vascular neurologist. Patients will return to the CSC/PSC site per protocol for data collection research visits at 3, 6, and 12 months, and the University of Alabama Birmingham (UAB) SDCC Survey Research Unit (SRU) will contact them by phone at these times (see Figure 4). No C3FIT intervention management will be provided at these visits, however, usual standard of stroke care will occur. If there are emergent needs, the patient will be referred to that site's emergency department, patient's family physician, or the physician PI at the site.

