
RED=Primary and Secondary Outcomes, BLACK=Additional Assessments by Data Coordinator SRU=UAB's Survey Research Unit ¹Complications monitored: Urinary tract infection, pneumonia, aspiration, deep vein thrombosis, skin breakdown, fall, myocardial infarction, depression, fever/other infection, and Afib. ²Risk factor profile: hypertension, diabetes, hyperlipidemia, smoking status, BMI, Afib, family history. *Will be collected if patient/caregiver are able and/or available.
													

Intervention Discontinuation Evaluations. If the patient or caregiver/family declines follow up in-person visits, we will offer follow-up phone or virtual evaluations for primary and secondary outcomes and other assessments. If consent not provided for this, no follow up will occur.

Special Instructions and Definitions of Evaluations. Evaluations to be performed include: SIS and smRS, PHQ-9 depression scale, Caregiver Strain Index, blood pressure, Cholesterol panel, Hemoglobin A1c, BMI, Smoking cessation, exercise assessment, diet assessment, readmission, and recurrence, and others (see Table 7).

Final On-Study Evaluations. On study evaluations will be completed by the Coordinator and the University of Alabama Birmingham (UAB) SDCC Survey Research Unit (SRU) to include SIS and smRS, and other assessments (see Table 5).

Concomitant Interventions. None.

Study Intervention Modifications. None.

Assessments. Table 7 identifies and defines the assessments and the timeframe for each measurement parameter.

Other Laboratory Studies. None.

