In addition to this primary analysis of the intermediate factors that is restricted to those not compliant/adherent at discharge, a supplemental analysis will assess the proportion compliant at 3, 6, and 12 months regardless of compliance at month 0 (i.e., proportion compliant/adherent in the entire population). This analysis will consider a mixed modeling approach with outcomes at 4 time points (0, 3, 6, and 12 months). The focus of this analysis will be on the change in the proportion compliant between month 0 and 12 months (but also reporting the change in the proportion to 3 and 6 months). In addition to assessing treatment differences in the change in the proportion, the treatment differences in the proportions at the 4 time points will be assessed.

For all six factors, analyses assessing the potential for bias from missingness will be performed using inverse probability weighting (for both the analysis restricted to those not compliant/adherent and for the entire population analysis). This will be conducted by first developing a logistic regression model estimated in all subjects predicting the probability of observing the 12-month observation. Predictors in the model will be site (with cluster randomization, implicitly including treatment effect), age, NHW race/ethnicity, sex, NIHSS and nSES. The inverse of this probability will be standardized by dividing by the sum of the inverses, standardizing the inverse probabilities to have the same sum as the sample size; hence, not inflating or deflating statistical power. The analysis for the factor will then be repeated using the inverse probability weights. Should the interpretation of results differ between the weighted and unweighted analyses, the primary interpretation will be based on the weighted analysis, and the weighted analysis will be the basis for figures and estimates in the manuscript will focus on the weighted results.

Effect modification will be assessed by age, sex, race/ethnicity, stroke sub-type, stroke severity (discharge NIHSS dichotomized at 0 to 1 versus 2+), and nSES.

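### The weight model in SAP 3.1 gives both arms one NIHSS effect, so for the factors measured at visits it would barely correct severity-related loss that is greater in CSC/PSC

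*Protocol*

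**What the plan says.** **Care by arm.** The protocol Summary, under Interventions, plans "coordination of post-acute in-home/facility care for ISPU Site patients, while CSC/PSC patients will be managed per standard CSC/PSC protocol".

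**Where outcomes are measured.** Section 5 of the ISPU-arm protocol places Stroke Mobile contact "During monthly visits in their home or care facility". Section 10.A says that ISPU patients and caregivers "will receive 12 in-home visits from Stroke Mobile". Section 5 of the CSC/PSC-arm protocol says: "Patients will return to the CSC/PSC site per protocol for data collection research visits at 3, 6, and 12 months". In Table 7 of each arm's protocol, blood pressure, LDL, HbA1c and smoking status are visit items without the survey-unit label.

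**Fallback.** Section 6 of both arm protocols says: "If the patient or caregiver/family declines follow up in-person visits, we will offer follow-up phone or virtual evaluations for primary and secondary outcomes".

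**Primary outcomes.** Section 10 of both arm protocols says that patients "will also be contacted via telephone by the blinded personnel at the UAB SDCC SRU to assess primary outcomes". Table 7 in each marks SIS and smRS at 3, 6 and 12 months as survey-unit items.

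**Missing-data check.** SAP 3.1 assesses bias from missingness by inverse probability weighting, using a logistic model for whether the 12-month value is observed: "Predictors in the model will be site (with cluster randomization, implicitly including treatment effect), age, NHW race/ethnicity, sex, NIHSS and nSES". No interaction is listed. If weighted and unweighted results lead to different interpretations, "the primary interpretation will be based on the weighted analysis". SAP 3.2 and 3.3 carry the weighting over to mRS and SIS.

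**Outcome models.** Four steps are reported: crude, then adding stroke severity, demographics and risk factors. Severity (SAP 2) covers discharge location, discharge mRS, discharge NIHSS in four categories, and stroke subtype. No step is named as primary.

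**The concern.** A disabled patient can be measured at home in ISPU but is expected to come back to the site in CSC/PSC. Loss of 12-month SBP, LDL, HbA1c or smoking data may therefore rise with severity more steeply in CSC/PSC. The site terms let the weight model match each site's overall retention, and so each arm's. They do not let the relation between NIHSS and retention differ by arm. A pooled slope is too shallow for CSC/PSC and too steep for ISPU. Severe patients stay under-represented in one arm and become over-represented in the other, and the two errors add in the arm difference.

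The SAP calls the six intermediate factors an integral part of the primary assessment, and the weighted result can take over the interpretation. A check that hardly reacts to this pattern would make the crude result look robust when it is not.

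**Working it through.** The documents give no retention by arm or severity, so there is no plan figure to reproduce. Every retention and outcome value below is assumed, to show how the specified weights behave.

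**Inputs**
- Four equal NIHSS groups (SAP 2 describes its categories as approximate quartiles).
- Assumed 12-month observation, mildest to most severe: CSC/PSC 92, 88, 80, 60%; ISPU 85% throughout.
- Assumed SBP control by group: 55, 52, 47, 36%, the same in both arms. There is no treatment effect, and the full-population value is (55+52+47+36)/4 = 47.5%.

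**1. Unweighted.** Arm mean = Σ r_g y_g / Σ r_g, where r_g is the proportion observed and y_g the outcome.
- CSC/PSC: (0.92×0.55 + 0.88×0.52 + 0.80×0.47 + 0.60×0.36)/3.20 = 1.5556/3.20 = 48.61%.
- ISPU: 47.50%.
- ISPU minus CSC/PSC: -1.11 points.

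**2. SAP-type weights.** A logistic model with arm and NIHSS-group main effects was fitted to the eight retention values, giving fitted probabilities f_g. Arm mean = Σ (r_g/f_g) y_g / Σ (r_g/f_g). A correct model has r_g/f_g = 1 in every group.

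| NIHSS group | CSC/PSC r/f | ISPU r/f |
|---|---|---|
| 1 (mildest) | 1.061 | 0.941 |
| 2 | 1.042 | 0.960 |
| 3 | 1.001 | 0.999 |
| 4 (most severe) | 0.870 | 1.118 |

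- CSC/PSC: 48.04%. ISPU: 47.01%. Difference: -1.03 points.
- Share of the bias left: 1.03/1.11 = 93%.

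The most severe group should be 25% of each arm. Unweighted, it is 18.8% of CSC/PSC (0.60/3.20) and 25% of ISPU. After weighting it is 21.9% and 27.8%. The gap between arms moves only from 6.2 to 5.9 points.

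**3. Arm-specific weights.** With an arm-by-NIHSS term, f_g = r_g. Both arms return 47.5% and the difference is 0.

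**4. Other assumed patterns (SBP control)**

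| CSC/PSC observed, % | ISPU observed, % | Unweighted | SAP weights | Share left |
|---|---|---|---|---|
| 92/88/80/60 | 85 flat | -1.11 | -1.03 | 93% |
| 90/85/80/70 | 85 flat | -0.65 | -0.60 | 92% |
| 92/88/80/60 | 90/90/88/86 | -0.98 | -0.72 | 73% |
| 90/85/80/70 | 90/90/88/86 | -0.52 | -0.35 | 67% |

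Other flat-ISPU patterns, from mild to extreme CSC/PSC gradients, left 80-96%. If control is unrelated to NIHSS, the bias is zero under any weights.

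**5. Steps 2-4.** In this set-up both arms have the same observed outcome within each NIHSS group. Any comparison that conditions on NIHSS gives 0, weighted or not.

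**6. Check with site terms.** A simulation used 21 sites of 60 patients, ICC 0.05, a steep pattern (CSC/PSC falling from 92% to 60%) and a continuous outcome with an 8-point gradient across NIHSS groups. The crude bias was -0.43 unweighted, -0.38 with the SAP weights and +0.03 with arm-specific weights. With NIHSS in the outcome model it was +0.03 under all three (Monte Carlo SE 0.02).

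**The case against.** **The primary outcomes do not depend on travel.** This stands. SIS and smRS are collected by telephone by the same blinded unit in both arms. A reader might infer that the mechanism carries over to SAP 3.2 and 3.3, because the weights do. Put through the first pattern, with assumed good-outcome rates of 95, 90, 75 and 35%, mRS gives -3.6 points unweighted and -3.4 weighted. That illustrates the weight model and does not forecast bias. More frequent contact in ISPU, and its extra payment for monthly visits, might raise telephone response, but nothing in the documents shows that. The example is also a 12-month cross-section, while SAP 3.2 and 3.3 contrast change from month 0. For the SIS change contrast, the simulation gave about -0.10 unweighted and -0.12 with the SAP weights (Monte Carlo SE 0.06), against a planned detectable difference of 2.7.

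**CSC/PSC patients are not strictly required to travel.** This also stands. The phone or virtual fallback can supply smoking status. It cannot supply LDL or HbA1c, which need a blood draw.

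**The protocol anticipates patients too ill to return.** A reader might take this wording in section 9 as evidence of differential loss. It is not: the same sentence gives those patients a floor score on SIS, and the next says that they do not count as missing. The SAP restates only mRS 6 for death. Neither rule covers SBP, LDL, HbA1c or smoking.

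**Models 2-4 already adjust for NIHSS, discharge location and discharge mRS** (the last is dropped only for the mRS outcome). Under the example's assumptions they remove the bias completely, so a reading that the plan's results as a whole stay biased is not supported. What remains is that the crude step is reported, weighted and unweighted, and no step is named as primary.

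**The bias is small against sampling error.** With 21 sites of 60, ICC 0.05 and a proportion near 50%, the SE of the arm difference is √[2×0.25×(1+59×0.05)/630] = 5.6 points. It is larger in the subgroup not controlled at discharge. This limits the practical weight of the point, but it does not make the check able to detect the pattern.

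**Conclusion.** The point holds for the factors measured at visits and for the crude model. The SAP 3.1 weights impose one NIHSS effect on both arms. If 12-month observation falls with severity more in CSC/PSC than in ISPU, they leave about two thirds to over 90% of the resulting crude bias. In the examples that is roughly -0.4 to -1.0 points of SBP control after weighting, against ISPU. Size and direction rest on assumed retention and on control being worse in more severe patients; the documents report neither. Weighted and unweighted crude results agreeing would therefore not show that missing data are harmless.

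Models 2-4 largely remove the bias if retention depends on severity through NIHSS and the treatment effect is constant. The documents do not support extending the travel mechanism directly to SIS and mRS. This is an inexpensive improvement to the missing-data check and does not show that the primary results will be biased.

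**What to change.** In SAP 3.1, fit the model for 12-month observation separately by arm, keeping site within arm, or add an arm-by-NIHSS interaction to the present model. Add discharge location and discharge mRS as predictors, since both are already SAP severity measures. The SAP 2 rule against using a variable as both outcome and predictor concerns a single model, so it does not bar discharge mRS from the separate weight model. State which of the four adjustment steps is primary, so that it is clear which weighted-unweighted comparison governs the interpretation.

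Using the same weight model in SAP 3.2 and 3.3 is precautionary.

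The change takes a sentence or two in the SAP and no new data. The price is a few more parameters and slightly more variable weights.
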